7. ADVERSE EVENTS

7.1. Definitions

The definitions below are based on International Council for Harmonization (ICH) guideline E2A, “Clinical Safety Data Management: Definitions and Standards for Expedited Reporting.”

7.1.1. Adverse Event

An AE is any untoward medical occurrence in a clinical trial subject administered a pharmaceutical product that does not necessarily have to have a causal relationship with this treatment. An AE can therefore be any unfavorable and unintended sign (including an abnormal laboratory finding), symptom, or disease temporally associated with the use of a medicinal product, whether or not related to the medicinal product.

- AEs may be new events.
- AEs may be preexisting events that increase in frequency, severity, or change in nature or seriousness during or as a consequence of participation in clinical studies.
- AEs may be pre- or posttreatment complications that occur as a result of a protocol-mandated procedure (such as a biopsy).
- AEs may be clinically significant changes from baseline in physical examination, laboratory tests, or other diagnostic investigation (e.g., laboratory results, x-ray findings).
- AEs may result from an overdose of the study medication.

Whenever possible, the diagnosis (rather than a series of terms related to a diagnosis) should be recorded as the AE term.

An AE does not include the following:

- Medical or surgical procedures (such as surgery, endoscopy, tooth extraction, or transfusion); the condition that leads to the procedure is an AE
- Pre-existing diseases or conditions present or detected before signing an informed consent form (ICF) that do not worsen
- Situations where an untoward medical occurrence has not occurred (such as hospitalization for elective surgery or social and/or convenience admissions)
- Overdose of either study medication or concomitant medication without any signs or symptoms, unless the subject is hospitalized for observation

Any medical condition or clinically significant laboratory abnormality with an onset date prior to the time the subject signed the ICF is considered to be preexisting and should be documented in the medical history CRF.

Pregnancy is not an AE; however, if a female subject becomes pregnant during the conduct of the study, the sponsor will be notified according to the procedures for SAE reporting as outlined in Section 7.4.3. Follow-up information regarding the outcome of the pregnancy and any fetal or neonatal sequelae will be obtained and documented.

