6.4.10.3. Medication and Medical History

A complete medical history will be taken during the screening visit (for De Novo subjects only) and will include evaluation of past and present cardiovascular, respiratory, GI, renal, hepatic, neurological, endocrine, lymphatic, hematologic, immunologic, dermatologic, psychiatric, genitourinary, substance abuse, surgical history, or any other diseases or disorders. Medical conditions will be recorded for 2 years prior to screening visit, along with the date of diagnosis, and any other relevant medical history that has an impact to the subject.

Medical events or conditions that arise or worsen in severity or frequency after the signing of the informed consent will be recorded as an AE.

All medications used during the 60 days prior to screening will be recorded in the source records. The only exception is drugs that were used to treat previous orthostatic hypotension; these will be recorded since the time of primary diagnosis.

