7.3.2. Causal Relationship to Study Medication

The Investigator’s assessment of causality is based on clinical judgment regarding the reasonable possibility that the study medication caused the event and may include consideration of some or all of the following factors:

- Possible alternative causes of the AE, including the disease under treatment, comorbid conditions, other medications, and environmental factors.
- The temporal association between drug exposure and onset of the AE.
- Whether the clinical or laboratory manifestations of the AE are consistent with known actions or toxicity of the study medication.
- Whether the AE resolved or improved with decreasing the dose or stopping the study medication (“de-challenge”) or recurred or worsened upon re-exposure to the study medication (“re-challenge”).

The causal relationship between the study medication and the AE will be described using one of the following categories:

- **Not Related:** Evidence exists that the AE has an etiology other than the study medication (such as a preexisting condition, underlying disease, intercurrent illness, or concomitant medication).
- **Related:** A temporal relationship exists between the event onset and administration of the study medication. It cannot be readily explained by the subject's clinical state or concomitant therapies and appears with some degree of certainty to be related based on the known therapeutic and pharmacologic actions of the drug. In case of cessation or reduction of the dose, the event abates or resolves and reappears upon re-challenge. It should be emphasized that ineffective treatment should not be considered as causally related in the context of AE reporting.

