8.2. Sample Size and Power

Assuming that 60% are eligible for randomization at the end of the 16-week OL period, approximately 258 subjects will be enrolled such that 154 subjects are expected to continue into the randomized treatment period. For the De Novo Group, the goal is to enroll at least 40% of MSA subjects.

The primary analysis will occur when all subjects in the Full analysis set (FAS) (Section 8.3.2) of double-blinded randomized withdrawal phase of the study have either completed the primary endpoint assessment (OHSA#1 and PGI-S at Week 6 post randomization) (V9, D155) or discontinued earlier and the database has been cleaned and locked. A sample size of 154 at randomization will provide an overall power of 90% to detect a difference of 25% (25% TD-9855 vs. 50% PBO) in the primary endpoint of proportion of subjects that meet the criteria of treatment failure at Week 6 (V9, D155) during the double-blind randomized withdrawal phase at two-sided alpha level of 0.05.

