8.6.2. Adverse Event Data

The AEs will be coded to the preferred terms (PTs) of the Medical Dictionary for Regulatory Activities (MedDRA[®]). Summaries will be presented by system organ class (SOC), PT, and severity (mild, moderate, severe), along with the number and percentage of subjects for whom events were reported.

For subjects continuing from OL phase to the double-blinded randomized withdrawal phase, an AE that begins on or after the date of the first dose of TD-9855 up to the date of last dose of TD-9855 in OL phase will be considered TEAE for OL phase. For subjects discontinuing the study during the OL phase, an AE that begins on or after the date of the first dose of TD-9855 and up to the date of last dose of TD-9855 plus 14 days follow-up period will be considered TEAE for OL phase.

In the double-blinded randomized withdrawal phase, a TEAE is defined as any AE that begins on or after the date of the first dose of study medication post randomization and up to the date of last dose of study medication plus 14 days follow-up period.

The number and percentage of subjects who experience TEAEs will be summarized. Summaries of TEAEs will include the following:

- All AEs, by SOC and PT and also by PT (by descending overall frequency)
- All AEs, by SOC, PT, and severity
- All study medication-related AEs, by SOC and PT
- All study medication-related AEs, by SOC, PT, and severity

- All AEs leading to premature discontinuation of study medication, by SOC and PT
- All AEs leading to temporary interruption of study medication, by SOC and PT
- All SAEs, by SOC and PT
- All study medication-related SAEs, by SOC and PT

All AEs reported will be listed by subject. A separate listing will be provided for all subjects who experience an SAE. Separate listings will also be provided for subjects who discontinued study treatment prematurely because of AEs and subjects who temporarily interrupted study treatment because of AEs. The AESIs, as described in Section 7.1.4, will be listed and summarized.

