9.1. Adverse Events

Adverse events are collected from signing of the informed consent form through the end of follow-up. Adverse events will be coded to the preferred terms of the Medical Dictionary for Regulatory Activities (MedDRA®, version 24.1).

A treatment-emergent adverse event (TEAE) will be defined as any AE that begins on or after the date of first dose of study drug up through 14 days after the date of last dose of study drug. AEs that begin more than 14 days after the date of last dose of study drug and AEs that begin during the period from obtaining informed consent to the start of administration of study drug will not be considered treatment-emergent and will be listed only.

The following AE summaries will be provided for each treatment period:

- TEAE overall summary
- TEAEs by preferred term
- TEAEs by system organ class and preferred term
- Moderate or severe TEAEs by system organ class and preferred term
- TEAEs by preferred term with frequency > 3% of safety analysis set subjects
- TEAEs by system organ class, preferred term, and severity
- Drug-related TEAEs by system organ class and preferred term
- Drug-related TEAEs by system organ class, preferred term, and severity
- Drug-related moderate or severe TEAEs by system organ class and preferred term
- Serious TEAEs by system organ class and preferred term
- Drug-related serious TEAEs by system organ class and preferred term
- TEAEs resulting in on-study deaths
- TEAEs leading to premature study drug discontinuation
- TEAEs leading to temporary interruption of study drug
- TEAEs of special interest by system organ class and preferred term (Section 9.1.1)

If no adverse events meeting a specific table definition were reported, the body of the table will contain only a statement that no events met the table definition.

The following AE listings will be provided:

- TEAEs
- AEs leading to premature study drug discontinuation
- AEs resulting in temporary interruption of study drug
- Serious adverse events
- Deaths
- Non-treatment-emergent adverse events
- Adverse events of special interest (Section 9.1.1)
- Adverse events for excluded site 27045 (Section 6.2.1)

9.1.1. [REDACTED]

[REDACTED]

- [REDACTED]
- [REDACTED]
- [REDACTED]
- [REDACTED]
- [REDACTED]
- [REDACTED]

[REDACTED]

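### In the randomized withdrawal period, return of nOH symptoms can be counted as a TEAE, so the subject-level any-event totals can understate an AE excess on TD-9855

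*Protocol*

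**What the plan says.** **What becomes an AE.** Protocol 7.1.1 includes worsening of something already present: "AEs may be preexisting events that increase in frequency, severity, or change in nature or seriousness during or as a consequence of participation". It leaves out "Pre-existing diseases or conditions present or detected before signing an informed consent form (ICF) that do not worsen". Protocol 6.4.10.3 adds a recording rule: "Medical events or conditions that arise or worsen in severity or frequency after the signing of the informed consent will be recorded as an AE". Protocol 6.4.10.5 (Neurological Examination) has a similar rule for symptoms that appear or get worse on treatment. None of these sections mentions nOH symptoms that come back once TD-9855 is stopped.

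**Relatedness.** Protocol 7.3.2 says "ineffective treatment should not be considered as causally related in the context of AE reporting". That settles how such an event is attributed. It does not say whether the event is recorded.

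**What becomes a TEAE.** For the randomized period, Protocol 8.6.2 says "a TEAE is defined as any AE that begins on or after the date of the first dose of study medication post randomization", continuing to 14 days after the last dose.

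**What is tabulated.** SAP 9.1 plans an overall TEAE summary, "TEAEs by system organ class and preferred term", moderate or severe and serious TEAEs by term, and "TEAEs leading to premature study drug discontinuation". It also plans several drug-related tables and an AESI table.

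**Expected failure rates.** Protocol 8.2 sizes the trial for "power of 90% to detect a difference of 25% (25% TD-9855 vs. 50% PBO").

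**Withdrawal reasons.** The lists in Protocol 6.8.2 and SAP 7.2 have no category for lack of efficacy.

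**The concern.** The randomized period is built so that more placebo subjects get their symptoms back. OHSA#1, the core of the primary endpoint, rates dizziness, lightheadedness and faintness, and these are also ordinary AE terms. If a relapse is reported as an AE, the subject counts once as an efficacy failure and again as having a TEAE. Because this happens more often on placebo, it raises the placebo totals and narrows or reverses any excess on TD-9855.

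The discontinuation summary has a further exposure. A subject who leaves because symptoms returned must be given some other reason, and adverse event is one of those available.

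Within Study 0170 this is the only controlled AE comparison, since the open-label period has no control arm. A reader who starts from the any-event line could conclude that TD-9855 adds no AE burden when it does. Counts by preferred term do not by themselves restore subject totals, because one subject can appear under several terms.

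**Working it through.** **1. The plan's own figure.** Inputs from Protocol 8.2 and 5.1: failure 25% and 50%, two-sided alpha 0.05, power 90%, 1:1 allocation. With pooled variance and no continuity correction:

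n per arm = [1.960 × √(2 × 0.375 × 0.625) + 1.2816 × √(0.25 × 0.75 + 0.50 × 0.50)]² / 0.25² = (1.342 + 0.848)² / 0.0625 ≈ 76.7, rounded up to 77.

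That gives 154 in total with power 90.1%, so the stated figure reproduces. (With a continuity correction the total would be 170.) Expected failures are 77 × 0.25 = 19.25 on TD-9855 and 77 × 0.50 = 38.5 on placebo, an excess of 19.25 on placebo.

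**2. Model for the any-TEAE row.** Let o be the risk of any TEAE other than relapse, q the failure rate, and f the share of failures recorded as an AE. With f equal in both arms and independence between relapse and other AEs:

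any-TEAE rate = 1 − (1 − o)(1 − f × q).

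The documents give q only. The values of o and f below are assumptions: o = 40% on TD-9855 and 30% on placebo, a true excess of 10 points.

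| f | TD-9855 | Placebo | Difference seen |
|---|---|---|---|
| 0 | 40.0% | 30.0% | +10 |
| 0.2 | 1 − 0.60 × 0.95 = 43.0% | 1 − 0.70 × 0.90 = 37.0% | +6 |
| 0.4 | 1 − 0.60 × 0.90 = 46.0% | 1 − 0.70 × 0.80 = 44.0% | +2 |
| 0.6 | 1 − 0.60 × 0.85 = 49.0% | 1 − 0.70 × 0.70 = 51.0% | −2 |

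**3. Break-even that does not depend on the background rate.** Let h be the chance that the drug itself causes an AE, acting on top of a background risk common to both arms. The any-TEAE rows are equal when (1 − h)(1 − 0.25f) = 1 − 0.50f, so h = 0.25f / (1 − 0.25f).

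| f | Extra placebo subjects with a relapse AE (19.25 × f) | h fully hidden |
|---|---|---|
| 0.1 | 1.9 | 2.6% |
| 0.25 | 4.8 | 6.7% |
| 0.5 | 9.6 | 14.3% |
| 1 | 19.25 | 33.3% |

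**4. Limits of these numbers.**
- The 25% and 50% are treatment failure, not symptomatic relapse. Protocol 8.5.1.1 counts withdrawals and missing Week 6 assessments as failures, and SAP 6.4.7 includes sponsor termination. They are upper bounds on relapse. Only the product f × q enters the formula, so halving both q values has the same effect as halving f.
- If relapse AEs occur mainly in subjects who already have another TEAE, the shift is smaller than shown.
- Nothing comparable can be computed for the moderate or severe, serious or discontinuation rows, because the documents give no rates for them.

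**The case against.** The case against has real substance.

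- **Recording is uncertain.** Symptomatic nOH is the disease under study and predates consent. A return to the pre-consent level is arguably a condition that has not worsened, and so not an AE. AEs come from staff observation or the subject's own report (Protocol 6.4.10.2), whereas failure needs only a 1-point worsening on each of two questionnaires. The recorded share could be small. This stands: a reader might infer that the comparison is certainly tilted toward TD-9855, and the documents show only that it can be.
- **Most tables are by term.** A reader might infer that the headline tables simply pool everything. In SAP 9.1 the moderate or severe and serious tables are by preferred term, and Protocol 8.6.2 has the discontinuation table by term too. Only the overall summary and the any-event rows pool. Rows such as dry mouth or nausea are not offset by relapse.
- **Other tables are protected.** Protocol 7.3.2 should keep most relapse out of the drug-related tables. The AESIs in Protocol 7.1.4 (supine hypertension, cardiovascular events, convulsion) are not nOH relapse. This stands.
- **Subject totals are recoverable.** AEs are listed by subject, so totals without nOH terms could be rebuilt. True, but a rebuild after unblinding would use a term list chosen with the results in view.
- **Removing terms can hide harm.** Protocol 1.4 names syncope as an important potential risk and dizziness as a possible one. This stands and shapes the fix.
- **Consent timing.** Rollovers from Study 0169 may have consented while on drug, De Novo subjects before any. A reader might infer an arm bias from this. Enrollment source precedes randomization, so uneven recording by source does not in itself favour an arm.
- **Redaction.** SAP 9.1.1 and parts of the appendices are blacked out, so a relevant rule there cannot be excluded.

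**Conclusion.** The point holds in a limited form. Under the readable text, returning nOH symptoms can be recorded as randomized-period TEAEs, the design expects more of them on placebo, and nothing separates them. The subject-level any-event rows of four summaries can therefore understate an AE excess on TD-9855.

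The size is not known. It is zero if no relapse is recorded as an AE. On the planned failure rates, a drug-caused AE risk of 2.6% is hidden if a tenth of failures are recorded, and 14.3% if half are. Both figures assume independence, equal recording in the arms, and failure rates that overstate relapse.

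A reader might also infer that this is the only controlled AE evidence for the drug. It is the only one inside Study 0170. Study 0169 was double-blind for 4 weeks (Protocol 4.1) and had a placebo group (SAP 6.1).

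The safety summaries are descriptive, and the primary efficacy test is not touched. This is an inexpensive improvement to reporting, not an error that invalidates the plan.

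**What to change.** In SAP 9.1, for the randomized withdrawal period:

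1. Keep the planned overall, moderate or severe, serious and discontinuation TEAE summaries as the main version.
2. Fix a list of nOH-symptom preferred terms before unblinding, for example dizziness, dizziness postural, presyncope, syncope and orthostatic hypotension.
3. For each of the four summaries, add (a) a version without the listed terms and (b) the listed terms alone, by arm.

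Part (b) is needed because syncope and dizziness are also possible effects of TD-9855. Showing them by arm keeps any drug-caused events in view.

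The cost is a term list and a few repeat tables, with no change to data collection. The drawback is that version (a), read on its own, omits drug-caused events under the listed terms, so it should always appear beside the main version and (b). If few relapses were recorded as AEs, the main version and (a) will nearly agree, and the question is closed.

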7.1.2. Serious Adverse Event

A serious adverse event (SAE) is defined as any untoward medical occurrence occurring at any dose that results in any of the following outcomes:

- Death
- Life-threatening situation. “Life threatening” refers to a situation in which the subject was at risk of death at the time of the event; it does not refer to an event which might have caused death if it were more severe.
- Inpatient hospitalization or prolongation of existing hospitalization

Note: “Inpatient hospitalization” means the subject has been formally admitted to a hospital for medical reasons, for any length of time. This may or may not be overnight. It does not include presentation and care within an emergency department. A scheduled hospitalization for a preexisting condition that has not worsened during participation in the study does not meet this criterion. Preplanned hospitalizations for an elective medical/surgical procedure, scheduled treatments, or routine check-ups do not meet this criterion. Complications that occur during hospitalizations are AEs. If a complication prolongs hospitalization, it is an SAE.

- Disability- A persistent or significant incapacity or substantial disruption of the ability to conduct normal life functions
- Congenital anomaly/birth defect in the offspring of a subject who received study medication
- Important medical events that may not result in death, be immediately life threatening, or require hospitalization, may be considered an SAE when, based upon appropriate medical judgment, they may jeopardize the subject and may require medical or surgical intervention to prevent one of the outcomes listed in this definition. Examples of such events are as follows:
 - Intensive treatment in an emergency room or at home for allergic bronchospasm
 - Blood dyscrasias or convulsions that do not result in hospitalization
 - Development of drug dependency or drug abuse

7.1.3. Additional Considerations for Serious Adverse Events

- Death is an outcome of an AE and not an AE in itself. Deaths of unknown cause for which the Investigator cannot identify a cause of death will be captured as death of unknown cause or death not otherwise specified.
- All deaths, regardless of cause, must be reported for subjects if the death occurs while the subject is participating in the study.

- “Occurring at any dose” does not imply that the subject is receiving study medication at the time of the event; dosing may have been given as treatment cycles or interrupted temporarily before the onset of the SAE but may have contributed to the event.

7.1.4. Adverse Event of Special Interest

- At each study visit, the Investigator (or designee) will specifically query for any AESIs. The following events are considered AESIs for this study:
 - Supine hypertension
 - Cardiovascular events (myocardial infarction, cerebrovascular accident, cardiac arrhythmia, congestive heart failure)
 - Convulsion
- All AESIs must be reported to Sponsor Clinical Safety and Pharmacovigilance within 24-hours of awareness by the Investigator or his/her designee.

The SAE/AESI Report Form must be completed in accordance with the SAE/AESI Report Form Completion Guidelines. If all information on the SAE/AESI Report Form is not available at the time of the initial report, follow-up AESI reports will be completed and submitted.

To report an AESI, complete and send the SAE/AESI Report Form to the following:

Theravance Biopharma Clinical Safety
[contact]
Email: [contact]

For medical questions regarding an AESI, contact the medical monitor by telephone as follows:

Medical Monitor Contact Information:
[contact] (US) /
[name] (Ireland)
Email: [contact]

For sites located in Mexico, Peru, Chile or Argentina:
Email: [contact]

7.2. Clinical Laboratory Abnormalities and Other Abnormal Assessments as Adverse Events or Serious Adverse Events

Abnormal laboratory findings (such as chemistry, hematology, or urinalysis) or other abnormal assessments (such as ECGs, x-rays, or vital signs) that are associated with signs and/or symptoms or are considered clinically significant in the judgment of the Investigator must be recorded as AEs or SAEs if they meet the definition of an AE (or SAE), as described in Section 7.1.1 (Adverse Event) and Section 7.1.2 (Serious Adverse Event).

If there are any AE questions, the Investigator is encouraged to contact the sponsor to discuss.

